Clinicaltrials.gov application number: NCT03666026

Title: *Improving Influenza Vaccination Delivery Across a Health System by the Electronic Health Records Patient Portal*

Unique Protocol ID17-001889

Submission Date: 12/14/2017

IRB Approval Date: 12/20/2017

Research Design and Methods: Describe in detail the design and methodology of the study.

SPECIFIC AIMS

The overall purpose of the RCTs is to evaluate the impact that R/R, delivered through the patient portal, could have on the flu immunization rates of UCLA Health patients. The intent is to ultimately take the information learned and create and disseminate an adaptable toolkit to other health systems.

Specific aims are

Aim #1: Adapt algorithms, educational messages, and protocols previously used for mailed or phone influenza vaccine R/R, to create a patient portal research platform. (Aim 1 is outlined in detail in IRB applications titled: Patient Portal - Patient Qualitative Interviews and Patient- Portal Provider Qualitative Interview)

Aim #2: Assess the impact of portal R/R and key design features upon flu vaccination rates and costs.

2a: Using a 4-arm RCT, clustering within practices (up to 55), compare the effectiveness of 1, 2, or 3 portal R/R's vs. 0 R/R's on influenza vaccination rates

Hyp. 2a.1 [Primary Outcome]: >1 portal R/R will increase vaccination rates vs. no R/R.

Hyp. 2a.2: More R/R messages will raise vaccination rates (3R/R > 2R/R > 1R/R > 0R/R).

OVERALL STUDY DESIGN

Subjects receiving the intervention will be patients at one of the primary care practices within UCLA Health's System (up to 55 practices), and will include patients of any age. A proportion of the patients from these practices will be selected to participate - i.e. those who meet the inclusion criteria. Randomization techniques will occur before each RCT.

Patients will either be randomized to receive 0 (control), 1, 2 or 3 flu reminder messages via the portal.

Number of Subjects

There are approx $n = 385,000$ patients in the primary care registry (RCT#1) who are active/inactive portal users and affiliated with the primary care practices of interest for this research, and will be randomized into either the control, 1, 2, or 3 reminder arms (for RCT #1).

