3. Add any other entries with the same address as any existing entry to the family
4. Add any other entries with the same primary phone as any existing entry to the family
5. Add any other entries with a patient ID matching the patient ID of guarantor as any existing entry to the family
6. Add any other entries with the same insurance member ID as any existing entry to the family
7. Repeat steps 2-6 until no new matches are found - this forms a single family
8. Repeat steps 1-7 on the remaining entries to build each additional family until all entries have been associated with a family.

Please note - when there were errors with the address and telephone number, these variables were not used to group families (ex. instances with 20+ entries with the same data for telephone number).

Definition of active portal user:

We can only send portal R/R messages to patients who have signed up for the portal. Since some patients sign up for the portal but never use it, we define an active portal user as a patient (or proxy on behalf of the patient) who has used the portal within 12m (~59% of UCLA patients), and who has logged in 1 or more times in the past 12 months (reference date for login activity will be selected by the research team and then working backwards by 365 days, example of a range 8/1/17 - 7/31/18 for RCT #1 excluding their initial activation login and any subsequent logins on the same date of account activation).

Selection of index patient from each family unit

1. If the family contains any active portal user per our definition above, the index patient is randomly selected from among these patients.
2. If the family contains no active portal users, the index patient is randomly selected from all patients in the family.

Selection of the index patient for primary analysis:

1. An active portal user per the definition above
2. The patient is affiliated with one of the primary care clinics of interest
3. The patient was randomly selected as the index patient in their family unit

We will assess primary intervention effects among eligible index patients, and secondary analyses for the entire primary care registry since the impact of the intervention reflects the extent of portal penetration and high

correlation that exists among members of the same family (n=385,000 patients in RCT #1; up to 480,000 patients for RCT #2, (ISS-generated data extraction: of 430,000; IP-generated data extraction of approximately 50,000 (MRNS only)

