Costs: We will assume that the actual per-dose vaccination costs (administration costs, vaccine costs, storage, etc.) are identical for intervention and comparison patients and equal to the average national reimbursement for an influenza vaccine dose. The difference in total costs between the study arms will be influenced by the total costs of implementing the intervention, the difference in vaccination rates within study arms, and the subsequent health care utilization by the population (which we can model from prior studies)

Effectiveness: For each RCT we will estimate effectiveness using model-based, standardized expected values (mean) at the end of each RCT. We will calculate incremental cost-effectiveness ratios (ICERs) for each intervention arm.

For example, to compare costs in RCT #1 for Arm 3 R/R's vs Arm 2 R/R's, the ICER is: $ICER (\text{Arms 3 R/R vs 2 R/R}) = (\text{costArm 3 R/R} - \text{costArm 2 R/R}) / (\text{Flu vaccine rateArm 3 R/R} - \text{Flu vaccine rateArm 2 R/R})$

In the numerator of the above equation, the costArm X is equal to [(# Flu vaccine doses given per study arm x average national vaccine reimbursement per dose) + average costs per patient in that Arm]. The denominator of the equation is the difference in model-based, standardized expected values at the end of the intervention.

STATISTICS AND ANALYTIC PLAN

Analytic Plan:

The primary outcome is receipt of influenza vaccine among eligible index patients comparing the effectiveness of 1, 2, or 3 MyChart flu reminders to zero MyChart flu reminders.

Secondary measures are receipt of influenza vaccine among all identified patients in the primary care registry (per the algorithm outlined above in the inclusion criteria), process metrics, # subsequent preventive visits, and costs.

Power Analysis:

Power was evaluated using a simulation study. We assumed a within-practice randomization plan, and expect at minimum the sample sizes reported in Table 3 (n=145,684). We further assumed, based on preliminary UCLA Health data, that influenza vaccination rates are 42% among portal users without receipt of any portal-based R/R, and 45%, 47% and 49% among users in the 1, 2, and 3 R/R arms. We estimate 1,248 portal user families per practice (we will select 1 subject per family), based on our estimated mean family size of 2.38 portal users per family, and up to 55 practices.

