Adjusting for clustering of patients in practices, and assuming an intraclass correlation (ICC) of 1% (consistent with previous work), this sample size provides >90% power to detect an overall difference of 5 percentage points between portal-based R/R (combining 1, 2, + 3 R/R arms) and 0 R/R arm for all users and subgroups of interest (age and race/ethnicity). The power for the subgroups corresponds to evaluating the treatment effect within each subgroup. These power analyses represent conservative estimates based on the available patient sample—we expect larger effect sizes based upon our prior R/R studies. An estimated number of index subjects is $1,248 \times 55 = 68,640$.

Statistical Analysis- Primary Outcome

Hyp. 2a.1: Patients receiving 1, 2, or 3 portal R/R will have higher influenza vaccination rates than 0 R/R.

Primary outcomes (patient receipt of flu vaccine) are binary; our main explanatory variable will be an indicator for the receipt of any portal-based R/R.

We will employ intent-to-treat analyses using mixed effects logistic regression models with practice random effects, an approach recommended for RCTs in which the goal is to estimate the causal effects of interventions on individuals, adjusted for patient correlation within practice. In addition to the treatment variable, the covariates in the model will include patient age (6m-17y, 18-64y, 65+y), race/ethnicity, gender, primary language, degree of portal use, flu vaccination in prior year, and practice type (internal medicine, family medicine, pediatric). This method performs well in situations where the number of observations per cluster is large and for unequal cluster sizes. Hypothesis tests will be two-sided and a p value < 0.05 will be considered statistically significant. We will use SAS v9.4 (SAS Institute Inc., Cary, NC).

Hyp 2a.2: More R/R messages will incrementally increase vaccine rates (3 R/R > 2 R/R > 1 R/R > 0 R/R): As above, we will use mixed effects logistic regression models.

The major difference for these analyses is that we will test for pairwise differences between consecutive study arms. With linear contrasts we can determine if each additional R/R increases vaccination rates. Bonferroni corrections will be applied to account for multiple comparisons. The expected sample size provides >90%

power to conservatively detect an OR of 1.13 between consecutive study arms (corresponding to a 3% increase in vaccination rates from the baseline rate of 42%).

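### Hyp. 2a.2: Holm in place of Bonferroni for the three consecutive-arm contrasts would be a nearly free gain in power for the 2-point steps; the planned method is valid

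*Combined protocol and SAP*

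**What the plan says.** In the Combined protocol and SAP, the Specific Aims state Hyp. 2a.2 as a full ordering: "More R/R messages will raise vaccination rates (3R/R > 2R/R > 1R/R > 0R/R". Under Statistical Analysis- Primary Outcome, the plan says of Hyp. 2a.2 that "we will test for pairwise differences between consecutive study arms", and that "With linear contrasts we can determine if each additional R/R increases vaccination rates". It then says "Bonferroni corrections will be applied to account for multiple comparisons". No step-down procedure is named and no divisor is printed. Four arms give three consecutive contrasts, so I take the divisor as 3. Tests are two-sided at 0.05.

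The same section claims more than 90% "power to conservatively detect an OR of 1.13 between consecutive study arms", which it equates with a 3-point rise from 42%. The Power Analysis assumes 42% with no reminder and "45%, 47% and 49% among users in the 1, 2, and 3 R/R arms". The assumed steps are therefore 3, 2 and 2 points. Power for the two 2-point steps is not reported.

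**The concern.** Under the plan's own rates the first contrast (1 vs 0) is almost certain to be significant. Bonferroni nevertheless holds the other two at 0.05/3, so part of the permitted 5% goes unused. Holm passes that unused part to the contrasts still open.

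Those are the contrasts that tell a health system whether a second or third reminder is worth sending, and the worked cost-effectiveness ratio in the plan is for 3 vs 2 reminders. They are also the smallest assumed effects. Hyp. 2a.2 is a secondary hypothesis; Hyp. 2a.1, the primary one, is a single test and is not touched.

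**Working it through.** **Inputs.** Rates 42%, 45%, 47%, 49% (Power Analysis). Equal allocation to four arms within practices (Methods and Study Procedures). 1,248 × 55 = 68,640 index patients, so 68,640 / 4 = 17,160 per arm. Two-sided 0.05; with divisor 3 (inferred), 0.05/3 = 0.01667 and critical z = 2.394.

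**The plan's own figure.** The odds ratio for 45% vs 42% is (0.45/0.55)/(0.42/0.58) = 1.130. With z = difference / √[(p₁(1−p₁) + p₂(1−p₂))/n], z = 0.03/√[(0.2436 + 0.2475)/17,160] = 5.608, and power = Φ(5.608 − 2.394) = 99.9%. This agrees with the stated bound of more than 90%.

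**The 2-point steps under Bonferroni.**
- 2 vs 1: OR (0.47/0.53)/(0.45/0.55) = 1.084; z = 0.02/√[(0.2475 + 0.2491)/17,160] = 3.718; power Φ(1.324) = 90.7%.
- 3 vs 2: OR (0.49/0.51)/(0.47/0.53) = 1.083; z = 0.02/√[(0.2491 + 0.2499)/17,160] = 3.709; power Φ(1.315) = 90.6%.

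So the bound holds for these steps too, narrowly.

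**Holm.** The smallest p-value is compared with 0.05/3, the next with 0.05/2 and the largest with 0.05, stopping at the first that fails. Four binomial arms were simulated (2,000,000 replicates) and both rules were applied to the same p-values, which builds in the correlation of about −0.5 between adjacent contrasts. No Bonferroni rejection was lost.

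| Index patients | Origin | Bonferroni, 2 vs 1 / 3 vs 2 | Holm | Gain per step | All three steps |
|---|---|---|---|---|---|
| 61,212 | 145,684 / 2.38 (assumption) | 86.8% / 86.6% | 94.0% / 93.8% | about 7 points | 73% → 88% |
| 68,640 | plan's index count | 90.7% / 90.6% | 96.1% / 96.0% | about 5.4 points | 81% → 92% |
| 95,441 | 385,000 × 0.59 / 2.38 (assumption) | 97.7% / 97.6% | 99.2% / 99.2% | about 1.6 points | 95.2% → 98.5% |
| 145,684 | printed in the Power Analysis, if it is the analysed number | 99.9% / 99.9% | 99.97% / 99.97% | about 0.1 point | 99.7% → 99.9% |

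The 61,212 and 95,441 rows come from separate runs of 1,000,000 replicates. The 0.59 is the share of patients who "used the portal within 12m (~59% of UCLA patients"; 2.38 is the plan's mean number of portal users per family.

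**Covariates.** The model adjusts for age, race/ethnicity, gender, language, portal use, "flu vaccination in prior year, and practice type". The documents give no figure for the resulting precision. Taking variance cuts of 10%, 20% and 30% as assumptions at 68,640:
- 10%: Bonferroni 93.6% / 93.5%, Holm 97.5% / 97.4%; gain about 4 points.
- 20%: Bonferroni 96.1% / 96.0%, Holm 98.6%; gain about 2.5 points.
- 30%: Bonferroni 98.0% / 97.9%, Holm 99.3%; gain about 1.4 points.

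**Clustering.** Randomization is within practice, so a common practice effect cancels between arms. Removing the 1% between-practice share of variance gives 91.0% and 96.2% for a 2-point step.

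**Familywise error at 68,640 (simulated).**

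| True rates | Bonferroni | Holm |
|---|---|---|
| 42/42/42/42 | 4.6% | 4.6% |
| 42/45/45/45 | 3.1% | 4.6% |
| 42/42/45/45 | 3.3% | 4.9% |
| 42/45/45/47 (one null step) | 1.7% | 4.6% |

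**Tests against intervals.** At 68,640 under the assumed rates, Holm rejects at least one step that Bonferroni does not in 10.7% of simulated trials. In each of these, the 98.3% (1 − 0.05/3) interval for that step includes no effect.

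**The case against.** The case for leaving the text alone is a reasonable one. Bonferroni is prespecified and valid, every consecutive step already exceeds 90% at the plan's index count, and this is a secondary hypothesis. All of that stands, and it is why this is an improvement only.

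The size of the gain is uncertain. The Power Analysis gives 145,684 as its minimum sample size, and the table it cites is not in the document. If that were the analysed number, the gain would be negligible. I rest on 68,640 because the primary analysis is restricted to one index patient per family and the plan gives that figure as its estimate of index subjects; the other rows show the dependence. Strong covariates would also shrink the gain.

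The objection about intervals also stands. Bonferroni keeps tests and intervals in agreement, which is a legitimate reason to prefer it. Holm with 98.3% intervals does not, in about one trial in nine, and those are exactly the trials in which Holm changes a decision. Holm also declares a single null step significant more often when the other two are real (about 4.6% against 1.7%), within the 5% limit.

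A reader might infer two stronger points, and the documents support neither:
- *That the claim of more than 90% power fails for the 2-point steps.* It does not at 68,640 (90.7% and 90.6%). It falls below 90% only at the assumed 61,212 without covariate gain.
- *That the 1% ICC cuts power severely.* A parallel-cluster design effect, 1 + (312 − 1) × 0.01 = 4.11 with 1,248/4 = 312 patients per practice and arm, would give about 28–29% under Bonferroni and 34% under Holm. It does not fit randomization within practices.

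**Conclusion.** A minor, inexpensive improvement; no stated figure is wrong. For testing, Holm is never worse than Bonferroni in power and stays within 5% familywise error under any dependence between the contrasts. At the plan's index count and rates it reduces the chance of missing a given 2-point step from about 9.4% to about 4%. Across the sample sizes considered, the gain runs from about 7 points down to about 0.1 point.

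This rests on a divisor of 3, the assumed rates, unadjusted two-proportion tests as an approximation to the mixed logistic model, and no loss of patients (the plan states none). The remark on OR 1.13 is one of wording: it is the largest of the three assumed steps, so calling it conservative does not describe the other two, but no conclusion changes.

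**What to change.** Before outcome data are examined, replace the Bonferroni sentence for Hyp. 2a.2 with:

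> Familywise error for the three consecutive contrasts (1 vs 0, 2 vs 1, 3 vs 2) will be controlled at 5% by the Holm procedure (smallest p-value against 0.05/3, next against 0.05/2, largest against 0.05, stopping at the first that fails). Significance will be declared from Holm-adjusted p-values; 98.3% simultaneous confidence intervals will be reported for estimation only and may include no effect for a contrast that Holm rejects.

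Optional, wording only: give power for the 2-point steps (OR about 1.08) beside OR 1.13.

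The cost is one sentence, or two with the option. Holm uses the three p-values the model already produces; arms, sample size, model and primary test stay as they are. The sponsor has to accept the test-interval mismatch and the higher single-null-step error described above. The subgroup section's Bonferroni rule can stand, but the plan should then say that the overall and subgroup analyses of Hyp. 2a.2 use different corrections.

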Many patients are members of the same family. As such, the research team will assemble family units (using household address, primary telephone number, patient ID of the guarantor, and insurance member ID as the variables of commonality to create these family units). For RCT 1, for each family, 1 individual will be randomly selected as the index patient. Only index patients who are also active portal users and affiliated with a primary care practice (criteria explained below) will have their data analyzed as part of the primary analysis plan. Secondary analyses will involve all study subjects.

Gender and age: We anticipate the gender distribution to be roughly equal. All ages of patients will be included in the study; however, patient will not receive a message until they are 6 months of age, as the flu vaccine is not recommended for those less than 6 months of age.

Racial and ethnic origin: There are no enrollment restrictions based on race/ethnicity.

Inclusion criteria

A patient at one of the clinics of interest within the UCLA Health System (up to 55 practices). An individual is deemed a primary care patient of the UCLA Health System through the following algorithm:

Assigned managed care patients (UCLAMG) + Attributed patients from other payers/ACOs

- ≥ 2 PCP visits in the past 3 years; or

- ≥1 PCP visit with preventive service code in past 1 year (99381-99397 or G0438/G0439)
- All visits cannot be urgent care visits (ie excludes visits after hours or on weekends, not by urgent care codes since UCLA does not bill accordingly)

Active patient: We decided to use the algorithm outlined above and currently approved and in place by the UCLA Health System as the research team believes it to be a generalizable model that could be applied to other health systems.

Exclusion criteria

Patients will be excluded from the overall study if they are not part of UCLA's primary care registry per the above algorithm detailed in the inclusion criteria.

Creating family units

An overall address field will be constructed from the data pull including the address, city, state, and zip code fields. Primary telephone number, patient ID of the guarantor and insurance member ID will be used as other variables in the process to create the family units. The following steps taken to create these family units is described below:

1. Start with a single entry in the contact data pull
2. Add any other entries with the same patient ID as any existing entry to the family

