Patient variables will include - age (6m-17y, 18-64y, 65+y), race/ethnicity, gender, primary language (by EHR), degree of portal use, and receipt of influenza vaccination in prior years. We recognize few UCLA patients have Medicaid; we will focus on low-income groups in the dissemination phase (Aim 3).

Dependent Measures

Vaccine Outcome: The primary outcome is influenza vaccination during the vaccination season as measured by analysis of EHR data. For children <9y who had not received prior influenza vaccination, the outcome will be at least 1 influenza vaccination.

Process Outcomes: These will include: (a) total # visits to the practice during the study time period, (b) # flu vaccine or nurse visits, and (c) missed opportunities. Visits will be measured by the EHR; using ICD-10/CPT codes to classify visits to primary care as preventive, acute/chronic, or nurse-vaccination. Missed opportunities are defined as # vaccine-eligible visits during which the patient did not receive an influenza vaccination. These process metrics will help assess how the intervention worked.

Additional Measures: see file: Summary of outcome measures RCT 1 which shows additional measures, grounded in the RE-AIM framework. Found in item 1.0 of this section.

Costs: Since the intervention is implemented centrally we assume no added practice costs. We also assume practice costs/vaccination from portal R/R is identical to standard practice costs/vaccination. We will assess the time and costs of study and implementation personnel and non-personnel costs, distinguishing planning costs from intervention costs. We will measure costs using a standardized time study/resource survey sent weekly to all individuals working on the study that delineates (a) the # hours spent for each individual, and (b) research vs implementation time. We will use national salary estimates by work code from the Bureau of Labor Statistics to value personnel time in standard rates. We will measure non-personnel costs EHR hardware, software, materials.

Cost and Cost Effectiveness

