Statistical Analysis- Subgroup analysis

We will test Hyp. 2a.1 and 2a.2 stratifying by age (6m-17y, 18-64y, 65+y) and race/ethnicity (Hispanic, NH Black, NH Asian, NH White). We will apply Bonferroni corrections to account for multiple comparisons.

Statistical Analysis- Process measures

Because other process measures (# visits, # vaccination or nurse visits, and # missed opportunities) are count outcomes, we will use negative binomial mixed effects models to compare incidence rates between arms, controlling for the patient and practice covariates mentioned above.

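### The visit and missed-opportunity models leave out each patient's pre-randomization visit count, a minor and cheaply remedied loss of precision on secondary process outcomes

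*Combined protocol and SAP*

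**What the plan says.** Under Dependent Measures, the process outcomes are "total # visits to the practice during the study time period", the number of flu vaccine or nurse visits, and missed opportunities (vaccine-eligible visits at which no influenza vaccine was given). Their stated purpose is to help explain how the intervention worked. The Analytic Plan lists process metrics among the secondary measures.

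Under Statistical Analysis- Process measures, the plan says "we will use negative binomial mixed effects models to compare incidence rates between arms". The adjustment set is given only by reference: "controlling for the patient and practice covariates mentioned above". Two earlier places list those covariates:

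- Statistical Analysis- Primary Outcome: "the covariates in the model will include patient age (6m-17y, 18-64y, 65+y), race/ethnicity, gender, primary language, degree of portal use, flu vaccination in prior year". The type of practice is listed there as well.
- Measures, Covariates: practice type, age, race/ethnicity and gender, then "primary language (by EHR), degree of portal use, and receipt of influenza vaccination in prior years".

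Neither list has a count of visits before randomization. Yet the Inclusion criteria attribute patients to the registry partly on "PCP visits in the past 3 years" (two or more) or on a preventive visit in the past year, and Dependent Measures says that visits are measured from the EHR. The plan states no mean, SD, expected effect or power for any process outcome.

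**The concern.** A patient's earlier attendance is an obvious candidate predictor of attendance during the season, and missed opportunities can accrue only at visits. The vaccination model adjusts for its own baseline counterpart, prior-year vaccination. The visit models have no counterpart, and no reason is given for the difference.

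Any effect of reminders on visits is likely to be small per patient, because most patients would be vaccinated, or not, whichever arm they were in. If visit counts vary widely, the planned model could give an interval too wide to show whether reminders work by bringing people in. A null result might then be read as evidence that they do not. What is at stake is the width of intervals on secondary outcomes. The comparison between arms stays unbiased.

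**Working it through.** **1. The plan's own figures.** 1,248 × 55 = 68,640 index patients, as stated. At 1:1:1:1 this is 17,160 per arm, so any reminder vs none is 51,480 vs 17,160. The Power Analysis assumes that "influenza vaccination rates are 42% among portal users without receipt of any portal-based R/R, and 45%, 47% and 49% among users" in the three reminder arms. The pooled effect is (45 + 47 + 49)/3 − 42 = 5 points, matching the stated "power to detect an overall difference of 5 percentage points between portal-based R/R". For vaccination, SE = sqrt(0.42×0.58/17,160 + 0.47×0.53/51,480) = 0.0044 and 0.05/0.0044 is about 11, so power exceeds 99.9%, consistent with the plan's claim of more than 90%. The odds ratio for 45% vs 42% is 1.13, as stated.

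**2. Implied effect on visits.** The plan gives none. Assume that each added vaccination brings exactly one added visit. The assumed rates then give, in visits per patient:

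- any reminder vs none: 0.05
- three vs none: 0.49 − 0.42 = 0.07
- consecutive arms: 0.03, 0.02 and 0.02

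**3. Assumptions that the documents do not supply.** Visit SD of 1 to 4 over the season; correlation rho between baseline count and outcome of 0 (not used), 0.3 or 0.5; analysis in index patients only; two-sided 5%; normal approximation. The design-effect penalty of a cluster-randomized trial is not applied, because randomization is within practice.

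**4. Formulas.** SE(pooled) = SD × sqrt(1/17,160 + 1/51,480) × sqrt(1 − rho²) = SD × 0.00881 × sqrt(1 − rho²). Power = Phi(effect/SE − 1.96). The SE multiplier is sqrt(0.91) = 0.954 at rho 0.3 (about 5% lower) and sqrt(0.75) = 0.866 at rho 0.5 (about 13% lower).

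**5. Pooled contrast, 0.05 visits.**

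| Assumed SD | SE, no baseline | SE, rho 0.5 | Power, no baseline | Power, rho 0.5 |
|---|---|---|---|---|
| 1 | 0.0088 | 0.0076 | >99.9% | >99.9% |
| 1.5 | 0.0132 | 0.0115 | 97% | 99% |
| 2 | 0.0176 | 0.0153 | 81% | 91% |
| 2.5 | 0.0220 | 0.0191 | 62% | 75% |
| 3 | 0.0264 | 0.0229 | 47% | 59% |
| 4 | 0.0353 | 0.0305 | 29% | 37% |

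At SD 2 and rho 0.3, power is about 85%.

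**6. Other contrasts at SD 2** (17,160 per arm, SE = 2 × sqrt(2/17,160) = 0.0216, or 0.0187 at rho 0.5). Three vs none, 0.07: 90% to 96%. Consecutive arms: 28% to 36% for 0.03 and 15% to 19% for 0.02, before any Bonferroni correction.

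**7. Cross-check in the planned model family.** One negative binomial dataset of 68,640 patients was simulated per scenario, without practice effects or the listed covariates, and fitted with and without log(1 + baseline visits). Power at the 0.05-visit effect went from 80% to 83% (mean 1.5, correlation 0.28), 81% to 89% (mean 1.5, correlation 0.47) and 61% to 74% (mean 2, correlation 0.51). This agrees with the normal approximation.

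**8. Sensitivity to the analysis population.** Take the 145,684 of the Power Analysis in place of index patients: 36,421 vs 109,263. With a family size of 2.38 and an assumed within-family correlation of 0 to 0.5, the variance multiplier is 1 to 1 + 1.38 × 0.5 = 1.69. Power for 0.05 visits without a baseline count is then 99% to 89% at SD 2 and 79% to 56% at SD 3.

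**The case against.** **Stronger readings that do not hold.** A reader might infer that 0.05 visits is the largest effect the trial could see, so that the planned model may miss even the best case. The plan's own rates contradict this: 0.05 is the pooled average, three reminders vs none gives 0.07, and at SD 2 that contrast has 90% power with no baseline term. The plan also says that it expects larger effects, and some children under 9 need two doses. A reader might equally want the term in the primary vaccination model. Nothing supports that: pooled power there already exceeds 99.9%, prior-year vaccination is already included, and another prognostic covariate would change the conditional odds ratio being estimated.

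**Population.** Number of Subjects says that secondary analyses take in all study subjects, and the section on selecting the index patient points them at the whole registry. The process-measure section does not restrict itself to index patients. Step 8 shows that power could be well above the index-patient figures. This stands, and the documents do not settle it.

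**Size of the gain.** The SD and correlation are assumed. At SD 1.5 or less the pooled contrast is well powered anyway; at SD 3 or 4 the added term still leaves power at 59% or 37%. Portal use and prior vaccination may already carry part of the information. The gain is therefore an upper bound, and it matters most around SD 2 to 2.5.

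**Outcomes covered.** The calculation is for total visits. No effect size is available for missed opportunities, and vaccination at a visit that would have happened anyway adds no visit.

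**Importance.** These are secondary outcomes with no stated hypothesis or power claim, and their model is already adjusted. That supports a low rating. It does not remove the omission or reverse the direction of the benefit.

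**Conclusion.** The point holds as a minor, optional improvement. The models for visits and missed opportunities omit the patient's own pre-randomization visit count, which can be drawn from the EHR visit data behind the registry algorithm. Including it would be expected to lower the SE by at most about 5% at correlation 0.3 and 13% at 0.5. In index patients, the largest gains in pooled power are of the order of 10 to 13 percentage points, at SD 2 to 3; the gain is small at SD 1.5 or below.

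This rests on one added visit per added vaccination, assumed SDs and correlations, and analysis in 68,640 index patients. Validity is not in question, and no conclusion about the primary outcome is affected.

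**What to change.** Add one sentence to Statistical Analysis- Process measures, before outcome data are seen so that the covariate cannot look data-driven:

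*Models for # visits and # missed opportunities also adjust for log(1 + number of PCP visits in the 12 months before randomization), extracted from the EHR for every patient, including assigned managed care patients and infants with a shorter look-back.*

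The last clause is needed because the registry algorithm applies thresholds and does not define a 12-month count, because assigned managed care patients appear to enter without a visit threshold, and because infants under 12 months cannot have a full look-back.

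Cost: one additional data extraction and one model parameter. Leave the primary vaccination model unchanged.
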